Date: February, 2022

STUDY PROTOCOL

**Administration of ONS Based on Purple Sweet Potato in Head and Neck Cancer Patients With
Radiotherapy**

[name]

**Universitas Brawijaya
Malang, East Java, Indonesia**

INTRODUCTION

A. Background

Cancer was the first and second most common cause of death before the age of 70 in 91 of 172 countries in the world in 2015 (Bray et al., 2018). One type of head and neck cancer (HNC), namely nasopharyngeal cancer, is ranked the 4th most common cancer in men and the 5th most common in both men and women (World Health Organization, 2019).

Cancer patients are at risk of experiencing malnutrition caused by changes in metabolism and pathophysiology of cancer itself, as well as side effects of cancer treatment or therapy. Malnutrition occurs in most (74%) of HNC patients with radiotherapy. Radiation to the head and neck area causes damage to the mucosa cells and salivary glands. It changes in taste, xerostomia, mucositis, pain, and hypophagia resulting in malnutrition. Its symptoms are decreased food intake, reduced body weight by 5%, decreased upper arm circumference, and reduced serum protein and albumin levels (Citak et al., 2019; Nicolini et al., 2013).

One of the nutritional interventions that can be given to prevent and treat malnutrition is administering oral nutritional supplements (ONS). ONS is part of nutritional support or medical nutrition therapy (MNT) in the form of oral food intake supplementation given for particular medical purposes in addition to a regular diet. The ONS form is usually ready-to-drink liquid or ready-to-boil powder but can also be used as a dessert or snack bar (Cederholm et al., 2017; Lochs et al., 2006). High protein ONS enriched with omega-3 in cancer patients can increase body weight, maintain muscle mass, reduce inflammatory response by lowering C-reactive protein (CRP) levels, and improve several domains of quality of life. Such as global health scores and cognitive and physical functioning (Schueren et al., 2018).

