- a. Assessing the effect of the ONS administration on nutritional status, which includes: energy and macronutrient intake, body weight, body mass index (BMI), mid-upper arm circumference (MUAC), muscle mass.
- b. Assessing the effect of giving ONS on physical function, namely grip strength.
- c. Assess the effect of the ONS administration on the patient's inflammatory response, which includes: CRP, neutrophils, lymphocytes, neutrophil/lymphocyte ratio (NLR) and IL-6.

RESEARCH METHODS

A. Research Design

This research is an experimental study using a Double-Blinded Randomized Controlled Trial design, with the intervention group receiving ONS containing immunonutrients with a composition consisting of purple yam flour, white egg flour, whey protein, olive oil, omega-3 powder, sugar, and creamer. In contrast, the control group received a standard ONS (iso-calorie) placebo with a composition of powdered skim milk, coconut oil, sugar, maltodextrin, and creamer. Each group received two packs of ONS/day @ 57 grams, brewed into 200 ml of formula with an energy content of ± 500 kcal for three weeks.

B. Population/Subject/Sample

The population in this study were MPA patients at RSUP [name], while the research subjects were these patients who met the following inclusion and exclusion criteria.

1. Inclusion criteria
 - a. Subjects diagnosed with advanced stage MPA (stages 3 and 4) who received radiotherapy or chemoradiotherapy, both as concurrent and adjuvant therapy.
 - b. Subjects aged 18-80 years.
 - c. Can consume food through a nasogastric tube (NGT) or orally.
 - d. Willing to participate in the research by signing informed consent. However, if the patient's general condition is terrible, the family is willing to sign an informed consent and help with the research.
2. Exclusion criteria
 - a. The subject has a milk or egg allergy
 - b. Subjects with comorbid renal impairment
 - c. Subjects with poor nutritional status with $BMI < 17.0 \text{ kg/m}^2$
 - d. Subject could not stand for weighing
3. Dropout criteria:
 - a. Subject died
 - b. Subjects withdrew from the study
 - c. Average ONS consumption $< 75\%$

The size of the study subjects was determined based on parameters of protein intake because one of the significant differences in the intervention and control formulas was the protein

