content (Arnold and Richter, 1989; Dahlan, 2013). The minimum number of subjects in this study was 22 subjects, with an additional 20% of 5 subjects, so the number of research subjects in each group was 27 or 54 subjects.

C. Location and Time of Research

The location of this research will be carried out at dr. Sardjito Yogyakarta, with research time, will be carried out for 14 months, starting from March 2022 to April 2023.

D. Research Parameters

This study has several research parameters, which include nutritional status in the form of changes in body weight, BMI, MUAC, body composition (muscle mass), and albumin; handgrip strength as physical function; and inflammatory response in the form of CRP, complete blood profile (leukocytes, neutrophils, lymphocytes, neutrophil/lymphocyte ratio).

E. Materials and Procedures

1. Research Materials

Materials for the manufacture of ONS immunonutrients

- 1) Purple sweet potato flour made from purple sweet potato flour of the Antin 3 variety
- 2) Ovobel white egg flour
- 3) Whey protein isolate 90
- 4) Bertolli brand virgin olive oil
- 5) Omega-3 powder from Novotech Nutrition USA
- 6) Powdered sugar obtained from refined sand from the Gulaku brand
- 7) Fiber Creme brand creamer

Materials for making standard ONS:

- 1) Low-fat milk brand Tropicana Slim
- 2) Barco brand coconut oil
- 3) Powdered sugar obtained from refined sand from the Gulaku brand
- 4) Fiber Crème brand creamer
- 5) Maltodextrin

2. Research Procedures

a. Preparation of Intervention Substances (ONS Immunonutrient formula and standard ONS)

Making ONS formulas containing either immunonutrients or standard ONS is done by mixing all the ingredients using a mixer with the amount of each ingredient according to the predetermined amount. The main ingredient in this formula is purple sweet potato flour, made by drying fresh purple sweet potatoes which have been blanched beforehand.

b. Clinical Trials

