For the measurement of research parameters in the form of nutritional status, it relatively does not pose a medical risk or trauma to the subject; while taking blood samples there is a risk in the form of phlebitis but this can be prevented by handling blood sampling, by a competent laboratory assistant. The product consumed by the subject was in the form of ONS or liquid food (such as milk) dense in nutrition (high in energy, high in protein, containing immunonutrients in the form of anthocyanin and omega 3), which was recommended by ESPEN as nutritional support for cancer patients undergoing radiotherapy. In addition, the consumption of products provided in the form of standard ONS or those containing immunonutrients carries a risk of digestive tract disorders, such as diarrhea, bloating, or constipation. If this happens, the subject will be referred to the doctor in charge of the study (DPJP or a radiation oncologist/dr. Sp. Onk. Rad) for examination and medication, the handling costs are the full responsibility of the researcher

F. Design of Data Processing/Analysis

The research data results were analyzed descriptively in the form of average \pm standard deviation if the data were normally distributed or median if the data were not normally distributed. The pre and post-test dependent variable data in each treatment and control group will be analyzed using a paired t-test if the data is normally distributed. Still, if the data is not normally distributed, it will be analyzed using Wilcoxon. As for the analysis of the difference between the pre and post test data then comparison between the control and intervention groups was carried out with the Independent t-test if the data was normally distributed, but if it was not normal, then it was analyzed using Mann Whitney.

G. Research Ethics

This research has received permission for ethical research feasibility from the Health Research Ethics Commission, Faculty of Medicine, Public Health and Nursing, Universitas Gadjah Mada Yogyakarta Indonesia with the number KE/FK/0996/EC/2021. Then before participating in the research, there will first be an explanation of the research's aims and objectives, the course of the research, and the benefits and risks that prospective research subjects may face. If the subject understands and agrees to participate in the study, the subject is asked to sign the informed consent that has been provided.

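### Taking less than 75% of the supplement makes a randomised patient a dropout, and no analysis of all randomised patients is named, so the compared groups may not be comparable

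*Combined protocol and SAP*

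**What the plan says.** - Research Methods, A describes a double-blind randomised trial with two arms. Each patient is given two 57 g packs a day for three weeks.
- Research Methods, B.3 gives three dropout criteria: death, withdrawal ("Subjects withdrew from the study") and "Average ONS consumption $< 75" per cent. It does not say what follows from meeting any of them.
- The rest of section B states that the sample size was "determined based on parameters of protein intake". It takes a minimum of 22 per group, "with an additional 20% of 5 subjects", to reach 27 per group and 54 in all.
- Section F applies paired tests within groups. For the pre-post differences it says that "comparison between the control and intervention groups was carried out with the Independent t-test if the data was normally distributed", with Mann-Whitney otherwise. It names no analysis population, no rule for a missing post-test value and no sensitivity analysis.
- Specific goal b is worded as "Assessing the effect of giving ONS on physical function, namely grip strength".

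**The concern.** Of the three criteria, only the consumption rule can remove a patient who is alive, consenting and measurable. Death is different, because it leaves no week-3 value under any analysis set. Average consumption over three weeks is a post-randomisation variable, so selecting on it gives up the protection of randomisation in two ways.

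First, consumption is related to prognosis. The Background attributes to radiation "changes in taste, xerostomia, mucositis, pain, and hypophagia resulting in malnutrition", and those symptoms bear directly on weight, arm circumference, muscle mass and intake. Second, consumption can depend on the product, since the two formulas differ in ingredients and protein. The documents do not say that either is less well tolerated, and section E.2.d gives the same digestive risks for both. If low consumption is more frequent in one arm, or arises for different reasons, the retained groups can differ in weight, grip strength, intake and inflammatory markers with no true effect. Blinding prevents knowing, selective removal. It does not stop taste or tolerability from affecting intake.

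Even with balanced exclusions the question changes. The effect of giving the supplement becomes the effect among those who took most of it. The rule also selects on a component of protein intake, the sizing parameter.

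**Working it through.** **The plan's own figure.** 22 x 1.20 = 26.4, rounded up to 27 per group, and 2 x 27 = 54. This reproduces. The allowance is 5 of 27 = 18.5% per arm, or 10 of 54. The base of 22 cannot be checked, because no difference, SD, alpha or power is given.

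**Protein tied to the rule.** The Background gives 15.8 g protein per 100 g of intervention powder. Then 2 x 57 g x 0.158 = 18.0 g/day, and 75% of that is 13.5 g/day. A retained intervention patient therefore has at least 13.5 g/day from the product on average. The control formula's protein content is not given.

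**Bias with no true effect.** The documents give no consumption rates and no correlation, so both are assumed. Let consumption and the pre-post change be bivariate normal with correlation rho, and remove patients below a consumption threshold, with probability p1 in one arm and p0 in the other. The expected spurious difference, in SDs of the change, is

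rho x [m(p1) - m(p0)], where m(p) = phi(z_p)/(1 - p) and z_p = Phi^-1(p).

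For 7/27 versus 3/27: m(0.259) = 0.437 and m(0.111) = 0.213, a difference of 0.224. Multiplying by rho = 0.3, 0.5 and 0.7 gives 0.067, 0.112 and 0.157 SD.

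The error rates below are simulated: 27 per arm, 200,000 replicates, and a two-sided 5% pooled t-test on the retained patients.

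| Exclusion probability | Bias (SD), rho = 0.3 / 0.5 / 0.7 | Type I error |
|---|---|---|
| 5/27 vs 5/27 | 0 | 5.0% to 5.1% |
| 6/27 vs 4/27 (22% vs 15%) | 0.033 / 0.056 / 0.078 | 5.1% / 5.4% / 5.9% |
| 7/27 vs 3/27 (26% vs 11%) | 0.067 / 0.112 / 0.157 | 5.6% / 6.6% / 8.6% |
| 40% vs 10% | 0.135 / 0.224 / 0.314 | 6.9% / 10.9% / 18.3% |

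The middle two rows spend exactly the planned total loss of 10. The last row is about 10.8 + 2.7 = 13.5 patients, above the allowance.

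In these rows the number removed varies from trial to trial. Removing exactly the stated number of lowest consumers leaves the bias almost unchanged but gives higher error rates: about 5.3% to 7.6% for 6 versus 4, and 5.8% to 10.2% for 7 versus 3. For 5 versus 5 the rate is 5.0% to 6.6%. Analysing all 27 per arm keeps the rate at about 5% throughout.

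**Change of question with balanced exclusion.** Suppose a proportion p = 0.20 is excluded and low consumers obtain a fraction h of the full benefit. The adherers-only estimate then overstates the effect of giving the supplement by 1/[(1 - p) + p x h] - 1:

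- h = 0.75: 1/0.95 - 1 = 5%
- h = 0.5: 1/0.90 - 1 = 11%
- h = 0: 1/0.80 - 1 = 25%

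**The case against.** The strongest reply is that exclusion is inferred. B.3 attaches no consequence to its list, and the 20% addition is not tied to the consumption rule and would fit death and withdrawal alone. That is correct as a reading of the text. But low consumption sits under the same heading as death and withdrawal, the sample is inflated for loss, and nothing says that these patients are kept. If the sponsor meant to keep them, the plan still has to say so, and the same wording does it.

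A second reply is that bias needs low consumption to differ between arms and to be related to outcome, and neither is documented. Both arms receive radiation, the products are iso-calorie and blinded, and patients fed by nasogastric tube are eligible, for whom taste matters less. If the extra exclusions in one arm are unrelated to prognosis, the bias is zero; a simulation of 7 versus 3 with the four extra removals made at random gives 0.00 SD. This stands, and it is why the size and direction are unknown. It does not show that the comparison is safe, because balance cannot be known in advance and measurements not taken cannot be recovered.

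Third, the scenarios assign all 10 planned losses to low consumption. With 4 versus 2 such exclusions the bias is only 0.04 to 0.08 SD. This is also fair, and the 40% versus 10% row should be read as an extreme.

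Finally, the general objective could be read as an efficacy question, and 25% overstatement assumes no benefit in patients who may take up to 74%. The per-protocol analysis in the fix serves the efficacy question, and the 5% and 11% figures cover partial benefit.

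**Conclusion.** The concern holds. A post-randomisation consumption threshold is a stated dropout criterion, and no analysis of all randomised patients is named anywhere. The comparison in section F may therefore be between groups that randomisation no longer makes comparable.

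Within the planned loss of 10 patients, the illustrative null bias runs from zero (balanced exclusions, or exclusions unrelated to outcome) to about 0.16 SD, with type I error up to about 8.6%, or about 10% if exact numbers are removed. Larger distortion needs more exclusion than the plan allows for. These figures rest on assumed splits and correlations and only show scale. The conclusion depends on the undefined analysis set, and it affects every between-group comparison. That exclusion is intended is the natural reading, not an explicit statement.

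**What to change.** 1. For follow-up and analysis, stop treating consumption below 75% as a dropout. Take the week-3 measurements on every randomised patient who is alive and willing, whatever was consumed.
2. State in section F that the main analysis includes all randomised patients in the group drawn from the envelope.
3. Keep the patients who took at least 75% as a secondary per-protocol analysis.
4. Report consumption, deaths and withdrawals by arm, and add a sensitivity analysis for missing week-3 values.

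Any rule on stopping the product stays as it is. The documents do not say whether the consumption criterion is such a rule, and the sponsor should clarify that.

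The cost is protocol and analysis wording, plus week-3 measurements on about 10 more patients at most if losses match the allowance. The main estimate may also be smaller. If 22 per arm was chosen for 80% power at two-sided 5% (an assumption), the standardised difference is (1.960 + 0.842) x sqrt(2/22) = 0.845. With 27 per arm analysed, power is then 87% with no dilution, 80% with 10% dilution, 72% with 18.5% (5 of 27 with no benefit) and 58% with 30%. These figures assume no missing week-3 values, so the sponsor should confirm that 54 patients still suffice.

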Another type of fatty acid is monounsaturated fatty acids (MUFA), which are more stable than PUFA and have health benefits (Vieira et al., 2015). Monounsaturated fatty acids are abundant in safflower oil and olive oil. Olive oil, besides containing MUFA, also contains high polyphenols, namely 150-400 mg/kg in m form virgin olive oil (Menendez and Lupu, 2006). In general, polyphenols have antioxidant, anti-inflammatory, antiallergic, antiatherogenic, antithrombotic and antimutagenic effects. Due to their ability to modulate cell death, olive oil polyphenols are also helpful as chemopreventive and therapeutic agents in cancer (Cárdeno et al., 2013; Gorzynik-Debicka et al., 2018).

Based on the results of preliminary research on the ONS formulation made from purple sweet potato, added whey protein, egg white powder, omega-3 powder, and olive oil, the ONS formula was obtained with an energy content of 440 kcal, 15.8 g protein (14% energy), 11.8 g fat (24% energy), carbohydrates 68.1 g (62% energy), dietary fibre 3.7 g, omega-3 164.6 mg and anthocyanins 32.8 mg per 100 g ONS powder. Combining these ingredients is expected to help increase food intake to positively affect the nutritional status and inflammatory response of HNC patients receiving radiotherapy.

B. Problem

Based on the above background, it appears that it is necessary to conduct a clinical trial of the effectiveness of purple yam-based ONS in head and neck cancer patients with radiotherapy, with research questions that can be formulated as follows:

"Is there any effect of local food-based oral nutritional supplements (ONS) containing immunonutrients (omega-3 and anthocyanins) on the nutritional status and inflammatory response of head and neck cancer patients receiving radiotherapy?"

C. Research Objectives

The general objectives and specific objectives of this study are described in the following points:

1. General purpose

The general objective of this study was to identify and analyze or study the effect of local food-based oral nutritional supplements (ONS) containing immunonutrients (omega-3 and anthocyanins) on the nutritional status and inflammatory response of head and neck cancer patients receiving radiotherapy.

2. Specific goals

This research has several specific objectives, which are described as follows:

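### Sample size rests on protein intake, which the product partly supplies and objective (a) (but not Section D) counts as nutritional status; no primary outcome is named

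*Combined protocol and SAP*

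**What the plan says.** **Sizing variable.** Research Methods B says the size was "determined based on parameters of protein intake because one of the significant differences in the intervention and control formulas was the protein" content. It continues: "The minimum number of subjects in this study was 22 subjects". Five are added for a 20% allowance, giving 27 per group and 54 in all.

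**Product.** Background A says that "the ONS formula was obtained with an energy content of 440 kcal, 15.8 g protein (14% energy") per 100 g of powder. Research Design A says: "Each group received two packs of ONS/day @ 57 grams, brewed into 200 ml of formula", with about 500 kcal. The control is described as iso-caloric and made with milk powder; its protein content is not given.

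**Two accounts of nutritional status.** Specific goal (a) covers "nutritional status, which includes: energy and macronutrient intake, body weight, body mass index (BMI), mid-upper arm circumference (MUAC), muscle mass". Section D, Research Parameters, instead gives "nutritional status in the form of changes in body weight, BMI, MUAC, body composition (muscle mass), and albumin", with no intake variable.

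**Other outcomes.** Goal (b) is grip strength. Goal (c) is "CRP, neutrophils, lymphocytes, neutrophil/lymphocyte ratio (NLR) and IL-6". Section D adds leukocytes.

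**Analysis.** Section F applies the same between-group comparison of pre-post differences (independent t-test or Mann-Whitney) throughout. No section names a primary outcome or a multiplicity rule. Section E.2.b keeps the product code with an external party until the data have been analysed.

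**The concern.** The research question asks about nutritional status and inflammatory response. Under goal (a), a higher total protein intake is itself a nutritional-status finding. If total intake includes the supplement, patients who drink a higher-protein product have a higher intake by construction, whatever happens to weight, BMI, MUAC or muscle mass. The reason given for sizing on intake is a property of the two powders, not an expected response in the patients.

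The second issue does not depend on the first. With a dozen outcomes on an equal footing, nothing in the plan settles which comparison carries the conclusion. A chance difference in one of them could become the headline. In either case the trial could report an effect on its main question that it has not shown.

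**Working it through.** **1. The plan's own figure.** 22 × 1.20 = 26.4, rounded up to 27 per group; 2 × 27 = 54. The allowance step reproduces. The base of 22 cannot be reproduced, because the difference, SD, alpha, sidedness and power are not stated.

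**2. Protein in the intervention packs** (Background A and Research Design A).
- Daily powder: 2 × 57 g = 114 g.
- Energy check: 114 × 440/100 = 501.6 kcal, which agrees with the stated 500 or so. The Background formula is therefore taken as the trial product.
- Protein: 114 × 15.8/100 = 18.0 g/day.
- At 75% consumption, the level below which "Average ONS consumption" makes a patient a dropout: 0.75 × 18.0 = 13.5 g/day.

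These are totals for the intervention arm. The built-in between-arm gap is the intervention product's protein minus the control product's, and the second term is unknown.

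**3. Could the product alone produce a significant intake difference?** Assumptions, none of them in the documents: the intervention is the higher-protein product; ordinary diet is unchanged in both arms; all packs are consumed; SD of change in protein intake is 10, 15 or 20 g/day; two-sided 5% t-test with 22 per arm (noncentral t).

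| Control protein as share of intervention | Gap, g/day | SD 10 | SD 15 | SD 20 |
|---|---|---|---|---|
| 0% | 18.0 | about 100% | 97% | 83% |
| 25% | 13.5 | 99% | 83% | 59% |
| 50% | 9.0 | 83% | 49% | 31% |
| 75% | 4.5 | 31% | 16% | 11% |

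At 75% consumption in both arms the gaps shrink by a quarter, and the SD 15 column becomes 83%, 59%, 31% and 11%. The range is so wide that it shows the artefact is possible, not that it is likely.

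**4. Outcome count, intake excluded.**
- Objectives: weight, BMI, MUAC, muscle mass, grip, CRP, neutrophils, lymphocytes, NLR, IL-6 = 10.
- Section D: weight, BMI, MUAC, muscle mass, albumin, grip, CRP, leukocytes, neutrophils, lymphocytes, NLR = 11.
- Union: the 10 plus albumin and leukocytes = 12.

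**5. Chance of at least one p<0.05 with no true effect** (assumed 5% per test).
- Independent: 1 − 0.95^12 = 0.46.
- Equicorrelated normal statistics, simulated: 0.40 at correlation 0.3, 0.32 at 0.5, 0.23 at 0.7.
- One pre-named outcome: 0.05.

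**6. What 22 per arm can detect on one outcome** (assumed two-sided 5%, t-test). Detectable difference at 80% power: 0.86 SD of the pre-post change. Power at 0.5 SD of change: 37%.

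**The case against.** **Total intake is a legitimate outcome.** The Background defines these supplements as part of oral intake, given on top of the usual diet, and hopes that they raise intake. On that footing total intake including the supplement measures what the product is meant to do. This stands. The issue is what a difference in total intake may be called, not whether to measure it.

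**Section D already leaves intake out.** Under its list a protein gap is not a nutritional-status result. This stands in part: the two sections disagree, and the plan does not say which governs.

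**The 18 g/day is not the contrast.** A reader might take it as the between-arm difference. The documents do not support that: the control contains milk powder and its protein is unstated. Nor do they say outright that supplement protein counts as intake; the sizing reason only implies it.

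**The withheld code is a safeguard.** It limits selection driven by the direction of effect, since the analyst should not know which group is which. It does not stop someone choosing, after the coded comparison, the outcome that separates the groups. The plan does not intend such a choice; it only leaves room for it.

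**Twelve overstates the separate chances.** Neither list has 12, BMI change is close to weight change rescaled, and NLR is built from neutrophils and lymphocytes, which leukocytes include. So 46% is an upper illustration, and a common correlation only approximates this structure.

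**Underpowering.** A reader might infer from the missing inputs that 22 per arm is too few. The documents do not show that. The inputs are undocumented, two references are cited for the method, and no target difference for any outcome is given to test 22 against.

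**Conclusion.** The point holds in two parts.

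- **Intake and nutritional status.** Goal (a) and Section D conflict. Under goal (a), a nutritional-status effect could be claimed from protein that the product delivers, with no change in body measures. The built-in part is at most 18.0 g/day (13.5 g/day at 75% consumption) less the control's protein. It rests on supplement protein being counted as intake and on the intervention being the higher-protein product. How likely this is to produce a significant result cannot be settled from the documents.
- **No primary outcome.** This needs neither of those assumptions. With no true effect, the chance of at least one nominally significant result is about 46% if the outcomes are independent and about 23% to 40% at common correlation 0.7 to 0.3, against 5% for one pre-named primary.

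The plan should be changed on both counts. The missing sizing inputs are a gap in documentation only.

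**What to change.** 1. **Reconcile goal (a) with Section D.** List energy and macronutrient intake as a separate delivery (exposure) outcome, not as nutritional status. Report protein and energy intake as ordinary diet, supplement and total. Add a sentence such as: *A difference in total intake shows delivery of the supplement and is not by itself an effect on nutritional status or inflammatory response.*
2. **Name one primary outcome** from Section D's nutritional-status or inflammatory parameters before any comparison by coded group. Date it and lodge it with the external party that holds the code. Treat all other outcomes as secondary, with between-arm 95% confidence intervals and no efficacy claim from any of them alone.

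**Cost.** Mainly wording, with no extra patients. The plan describes no dietary recording method. If none exists, splitting intake by source needs one, at two records for each of 54 patients (2 × 54 = 108). A protein-intake difference could no longer carry the nutritional-status claim. The single primary would have limited power: under the assumed two-sided 5% test with 22 per arm, 37% at 0.5 SD of change, and 80% only at about 0.86 SD. Those figures are this review's assumptions and should not be written into the plan as the authors' own inputs.

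### Does adding 20% to 22, to reach 27 per group, leave the trial short if 20% of the subjects drop out?

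*Combined protocol and SAP*

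**What the plan says.** The sample size is given at the end of section B of the Research Methods (Population/Subject/Sample). The basis is named first: "The size of the study subjects was determined based on parameters of protein intake". The count follows: "The minimum number of subjects in this study was 22 subjects, with an additional 20% of 5 subjects", and then "so the number of research subjects in each group was 27 or 54 subjects". The 22 is not itself labelled as per group, but it must be, because 22 + 5 = 27 and 27 is given per group.

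The sentence does not say what the five extra subjects are for. Item 3 of the same section, headed "Dropout criteria", comes immediately before the sample size text. It lists death, withdrawal and a mean intake of the supplement under 75%, and gives no expected rate for any of them. The plan also gives no significance level, power, difference or standard deviation behind the 22.

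**The concern.** The usual way to allow for a dropout proportion d is to divide the required number by 1 − d, because the losses come out of those enrolled. Multiplying by 1 + d is a familiar slip that gives too small a number. Here 22 is called a minimum, the addition is 20%, and the dropout criteria stand just above it. A reader will naturally take the 20% as a loss allowance and see that it was applied to the 22 to be kept and not to the number enrolled.

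If that were a real error, the trial could lose the proportion it had planned for and still finish below its minimum, with less power than intended. Because low intake of the supplement counts as dropout, losses of this kind are plausible.

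**Working it through.** **Inputs, all from section B:** minimum 22 per group; addition 20%, given as 5; final size 27 per group and 54 in total. Not given: the purpose of the addition, an expected dropout rate, significance level, power, difference and standard deviation.

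**1. Reproduce the plan's figure.** 0.20 × 22 = 4.4, rounded up to 5. Then 22 + 5 = 27 and 2 × 27 = 54. Equivalently, 22 × 1.20 = 26.4, rounded up to 27. The figures agree with the text.

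**2. The other convention.** 22/(1 − 0.20) = 22/0.80 = 27.5, rounded up to 28 per group, or 56 in total. The two conventions differ by 1 subject per group and 2 overall.

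**3. What 27 per group tolerates in whole subjects.** 20% of 27 is 5.4.

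| Lost per group | Proportion of 27 | Remaining | Within 20%? |
|---|---|---|---|
| 5 | 5/27 = 18.5% | 22 | yes |
| 6 | 6/27 = 22.2% | 21 | no |

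No loss rate between 18.5% and 22.2% can occur in a group of 27. At most 5 of 27, and at most 20% of 27, are therefore the same condition, and both leave 22 or more.

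**4. The expected-value version.** If 20% is the average loss, the expected number kept is 27 × 0.80 = 21.6, which is 22 − 21.6 = 0.4 short. To put a size on this, assume a two-sample t-test at two-sided 5% and that 22 per group was set for either 80% or 90% power. The plan states neither.

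| Power assumed at 22 | Standardised difference implied | Power at 21.6 | Fall |
|---|---|---|---|
| 80% | 0.865 | 79.2% | 0.8 points |
| 90% | 1.001 | 89.4% | 0.6 points |

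At 21 per group the values would be 78.1% and 88.6%. That case needs a sixth loss, which step 3 shows to be more than 20%, so it does not describe a 20% allowance.

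**5. Chance of keeping 22.** If each subject independently has a 20% risk of loss, a group keeps at least 22 with probability 0.54 when 27 are enrolled and 0.68 when 28 are enrolled. The number from the usual formula still falls short in 1 − 0.68 = 0.32 of groups. Neither convention guarantees the minimum.

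**The case for a change.** The best case for the concern is that the dropout reading is the only sensible one. A minimum with a margin on top, placed directly after a list of dropout criteria, has no other evident purpose in the document. On that reading the planning question is what happens on average at a 20% risk, and the answer is 21.6, not 22. The probability of holding 22 per group also rises from 0.54 to 0.68 with one more subject.

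The expected-value arithmetic stands, and so does the observation that the plan does not label the addition. The step from there to an error does not. The words "with an additional 20% of 5 subjects" promise an addition of 20%, and at least that was added, since 5/22 = 22.7%. Nowhere does the plan undertake to keep 22 at an average loss of 20%, so the shortfall is measured against a target that the reader has supplied. Rewriting the sentence as a tolerance of 5 in 27 would keep 27 and 54 and permit exactly the same losses as a limit of 20%. It would change a label and no result.

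The whole-subject argument holds within each group. Across the trial, 20% of 54 is 10.8, so at most 10 losses, which leaves 54 − 10 = 44 = 2 × 22. Those losses could fall unevenly between the groups, but neither inflation formula prevents that.

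**Conclusion.** The concern does not hold. The sum in section B is correct for what it says, no stated loss rate is missed, and any loss of up to 20% within a group of 27 leaves at least the minimum of 22. What remains is a choice between two inflation conventions that differ by one subject per group. In expectation it amounts to 0.4 of a subject per group, or 0.6 to 0.8 percentage points of power.

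The power figures rest on the assumed test, significance level and 80% or 90% starting power. The conclusion itself needs none of these, only the 22, the 5 and the 27. It does not vouch for the 22, which cannot be checked because its inputs are not given. That is a separate matter, and the base used for the 20% has no bearing on it.
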